6.5. Concomitant therapy

At each study visit, the investigator or delegate should question the participant about any medications/products taken and vaccinations received by the participant.

The following concomitant medications/products/vaccines must be recorded in the eCRF:

- All concomitant vaccines/medications/products associated with an AE, except vitamins and dietary supplements, administered following the first dose of study vaccine (Day 1 to Day 43).
- Any concomitant medications/products/vaccines leading to the withdrawal or non-eligibility of the participant from the study.
- Any concomitant medications/products/vaccines relevant to an SAE/potential immune-mediated disease (pIMD) to be reported as per protocol or administered at any time during the study period for the treatment of an SAE/pIMD. Concomitant medications relevant to SAEs and pIMD must be recorded on the Expedited Adverse Events report.

An antipyretic is considered prophylactic when it is given in the absence of fever and any other symptom, to prevent fever from occurring.

The PPD Medical Monitor should be contacted if there are any questions regarding concomitant or prior therapy.

6.6. Dose modification

Not applicable

6.7. Intervention after the end of the study

No intervention is planned after participants complete the study. No additional care will be provided to participants after they complete or discontinue the study.

7. DISCONTINUATION OF STUDY INTERVENTION AND PARTICIPANT DISCONTINUATION/WITHDRAWAL

7.1. Discontinuation of study intervention

'Discontinuation' of study vaccine/product means any participant who has not received all planned doses of vaccine/product. A participant who discontinued study vaccine/product should be encouraged to, if deemed appropriate by the investigator, continue other study procedures (e.g. safety or immunogenicity) if planned in the study protocol.

The primary reason for premature discontinuation of the study vaccine/product will be documented on the eCRF based on the following:

- Adverse event requiring expedited reporting to GSK
- Unsolicited non-SAE
- Solicited AE
- Protocol deviation
- Not willing to be vaccinated
- Other (specify).

7.1.1. Criteria for temporary delay for enrollment and/or vaccination

Vaccination may be postponed within the permitted time interval until transient circumstances cited below are resolved:

- Acute disease and/or fever at the time of vaccination. Refer to the SoA (Section 1.3) for fever definition and preferred location for measuring temperature in this study.
- Participants with a minor illness (such as mild diarrhea, mild upper respiratory infection) without fever may be enrolled and/or vaccinated at the discretion of the investigator.
- Use of antipyretics and/or analgesics and/or antibiotics within 12 hours prior to vaccination.

7.1.2. Contraindications to subsequent vaccine(s) administration

Participants must be evaluated to confirm they are eligible for subsequent vaccination before administering each additional study vaccine dose.

Participants who meet any of the criteria listed below or criteria listed in Sections 5.2.1 and 5.2.2 should not receive additional vaccinations. However, these participants should be encouraged to continue other study procedures at the discretion of the investigator (Section 10.3.8.2). The relevant criteria for discontinuing vaccination must be recorded in the eCRF.

- Participants who experience any SAE judged to be possibly or probably related to study vaccine or non-study vaccines, including hypersensitivity reactions.
- Participants who develop any new condition which, in the opinion of the investigator, may pose additional risk to the participant if he/she continues to participate in the study.
- Anaphylaxis following the administration of vaccine/product.
- Any condition that in the judgment of the investigator would make intramuscular injection unsafe.
- Occurrence of a new pIMD that, in the opinion of the investigator, expose the participant to unacceptable risk from subsequent vaccination. In such cases, the investigator should use his/her clinical judgment prior to administering the next dose of the vaccine/product. Refer to Section 10.3.5.1 for the definition of pIMDs.

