5.2.1. Medical conditions

1. Current diagnosis or history of autoimmune disorder(s). Refer to [Table 19](#) for conditions that constitute autoimmune disorder(s).
2. History of any reaction or hypersensitivity likely to be exacerbated by any component of the vaccine.
3. Hypersensitivity to latex.
4. Acute or chronic clinically significant pulmonary, cardiovascular, hepatic or renal functional abnormality that appears uncontrolled, as determined by history or physical examination.
5. Any confirmed or suspected immunosuppressive or immunodeficient condition, based on medical history and physical examination (no laboratory testing required).
6. Recurrent history or uncontrolled neurological disorders or seizures.
7. History of Guillain-Barré syndrome.
8. Diagnosed with narcolepsy; or history of narcolepsy in a participant's parent, sibling or child.
9. Diagnosed with cancer, or treatment for cancer within 3 years.
 - Persons with a history of cancer who are disease-free without treatment for 3 years or more are eligible.
 - Persons with a history of histologically-confirmed basal cell carcinoma of the skin successfully treated with local excision only are accepted and are eligible, but other histologic types of skin cancer are exclusionary.
 - Women who are disease-free 3 years or more after treatment for breast cancer and receiving long-term prophylaxis (for example, with tamoxifen) are eligible.
10. Documented human immunodeficiency virus-positive participant.
11. Any clinically significant* hematological laboratory abnormality.

*The investigator should use his/her clinical judgement to decide which abnormalities are clinically significant.

12. Bedridden participants.
13. Any other clinical condition that, in the opinion of the investigator, might pose additional risk to the participant due to participation in the study.

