10.3.5.1. Potential immune-mediated diseases

Potential immune-mediated diseases are a subset of AESIs that include autoimmune diseases and other inflammatory and/or neurologic disorders of interest which may or may not have an autoimmune etiology. Adverse events that need to be recorded and reported as pIMDs include those listed in the [Table 19](#).

However, the investigator will exercise his/her medical and scientific judgement to determine whether other diseases have an autoimmune origin (i.e. pathophysiology involving systemic or organ-specific pathogenic autoantibodies) and should also be recorded as a pIMD.

Table 19 List of potential immune-mediated diseases (pIMDs) (Amended 22 February 2022)

Medical Concept	Additional Notes
Blood disorders and coagulopathies	
Antiphospholipid syndrome	
Autoimmune aplastic anemia	
Autoimmune hemolytic anemia	
 Includes warm antibody hemolytic anemia and cold antibody hemolytic anemia
Autoimmune lymphoproliferative syndrome (ALPS)	
Autoimmune neutropenia	
Autoimmune pancytopenia	
Autoimmune thrombocytopenia	
 Frequently used related terms include: "autoimmune thrombocytopenic purpura", "idiopathic thrombocytopenic purpura (ITP)", "idiopathic immune thrombocytopenia", "primary immune thrombocytopenia".
Evans syndrome	
Pernicious anemia	

Medical Concept	Additional Notes
Thrombosis with thrombocytopenia syndrome (TTS)	
Thrombotic thrombocytopenic purpura	
 Also known as "Moschcowitz-syndrome" or "microangiopathic hemolytic anemia"
Cardio-pulmonary inflammatory disorders	
Idiopathic Myocarditis/Pericarditis	Including but not limited to: 
 Autoimmune / Immune-mediated myocarditis Autoimmune / Immune-mediated pericarditis Giant cell myocarditis
Idiopathic pulmonary fibrosis	Including but not limited to: 
 Idiopathic interstitial pneumonia (frequently used related terms include "Interstitial lung disease", "Pulmonary fibrosis", "Immune-mediated pneumonitis") Pleuroparenchymal fibroelastosis (PPFE)
Pulmonary alveolar proteinosis (PAP)	
 Frequently used related terms include: "pulmonary alveolar lipoproteinosis", "phospholipidosis"
Endocrine disorders	
Addison's disease	

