Protocol Deviation	Enr	Rand	Exp	FAS1	FAS2	PPS1	PPS2	mPPS1	mPPS2	MNPPS1	MNPPS2	MNmPPS1	MNmPPS2
Invalid informed consent or fraud in data	X	X	X	X	X	X	X	X	X	X	X	X	X
Incorrect treatment number provided at V2						X		X		X		X	
Unblinding of subject by sponsor/CRO personnel not done per study procedures at V1						X	X	X	X	X	X	X	X
Unblinding of subject by sponsor/CRO personnel not done per study procedures at V2						X		X		X		X	
Investigational vaccine administrated at V1 Day 1 even though subject met exclusion						X	X	X	X	X	X	X	X
Persistent inadequate source documents management after re-education**							X		X		X		X
Vaccine temperature deviation at V1						X	X	X	X	X	X	X	X
Vaccine temperature deviation at V2						X		X		X		X	
Inclusion/Exclusion criteria not meet						X	X	X	X	X	X	X	X
Study vaccine dose not administered according to protocol for V1: Wrong site/route injection/, wrong reconstitution, incorrect volume, Expired vaccine administered						X	X	X	X	X	X	X	X
Study vaccine dose not administered according to protocol for V2: Wrong site/route injection, wrong reconstitution, incorrect volume, Expired vaccine administered						X		X		X		X	

Protocol Deviation	Enr	Rand	Exp	FAS1	FAS2	PPS1	PPS2	mPPS1	mPPS2	MNPPS1	MNPPS2	MNmPPS1	MNmPPS2
Subsequent vaccine administered while contraindicated at V1						X	X	X	X	X	X	X	X
Subsequent vaccine administered while contraindicated at V2						X		X		X		X	
Incomplete treatment course V1						X	X	X	X	X	X	X	X
Incomplete treatment course V2						X		X		X		X	
Vaccination date at V2 done outside of the interval between V1 and V2 of 18-25 Days						X				X			
Vaccination date at V2 done outside of the interval between V1 and V2 of 18-32 Days									X			X	
Serological results collected but not available at V1						X	X	X	X	X	X	X	X
Blood sample at V1: not taken, not available, low serum volume, Lab error (spinning ...), temperature deviation						X	X	X	X	X	X	X	X
Blood sample at V2: not taken, not available, low serum volume, Lab error (spinning ...), temperature deviation					X*		X		X		X		X
Blood sample at V3: not taken, not available, low serum volume, Lab error (spinning ...), temperature deviation				X*		X		X		X		X	
Blood sample collection at V2 done outside of the interval between V1 and V2 of 18-25 Days							X				X		

Protocol Deviation	Enr	Rand	Exp	FAS1	FAS2	PPS1	PPS2	mPPS1	mPPS2	MNPPS1	MNPPS2	MNmPPS1	MNmPPS2
Blood sample collection at V2 done outside of the interval between V1 and V2 of 18-32 Days									X				X

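### Protocol Section 7.1.2 gives two inconsistent instructions on dose 2 after a Table 19 condition that arises between the doses

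*Protocol*

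**What the plan says.** The lead-in to Protocol Section 7.1.2 reads: "Participants who meet any of the criteria listed below or criteria listed in Sections 5.2.1 and 5.2.2 should not receive additional vaccinations". The exclusion criteria are therefore not only an entry check; they are applied again before dose 2.

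Protocol Section 5.2.1, criterion 1, is "Current diagnosis or history of autoimmune disorder(s", and it sends the reader to Table 19 "for conditions that constitute autoimmune disorder(s". Criteria 7 and 8 of the same list name Guillain-Barré syndrome and narcolepsy. None of the three mentions the investigator's opinion.

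Table 19 is the pIMD list. Section 10.3.5.1 introduces it with "Adverse events that need to be recorded and reported as pIMDs include those listed in the" table. It also lets the investigator record other diseases of autoimmune origin as pIMDs, and notes that pIMDs need not have an autoimmune cause.

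The last bullet of Section 7.1.2 lists, as a reason to withhold further doses, "Occurrence of a new pIMD that, in the opinion of the investigator, expose the participant to unacceptable risk from subsequent vaccination". It continues: "In such cases, the investigator should use his/her clinical judgment prior to administering the next dose of the vaccine/product".

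On the analysis side, Protocol Section 9.3.1.1 says that a participant who meets a Section 7.1.2 criterion may be eliminated from the per-protocol sets. SAP Table 9 has a row "Subsequent vaccine administered while contraindicated at V2", which excludes from PPS1, mPPS1, MNPPS1 and MNmPPS1.

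**The concern.** Suppose a Table 19 condition starts between the doses and the investigator does not regard it as an unacceptable risk. By the cross-reference to Section 5.2.1 the participant should not be dosed again. By the last bullet of Section 7.1.2 the decision appears to be open. Two sites could act differently on the same event and both cite the protocol.

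Protocol Section 10.3.5 makes pIMDs the only adverse events of special interest collected, and Table 3 puts them among the primary safety endpoints. Whether such a participant is re-exposed, and so contributes safety data after dose 2, should not depend on which sentence the site reads. Section 7.1.2 also requires the relevant stopping criterion to be recorded in the eCRF, so inconsistent readings would enter the data.

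The second stake is the primary immunogenicity set. If dose 2 is given, whether it was given while contraindicated turns on the same unresolved wording.

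**Working it through.** No figure in the plan bears directly on this, so the main check sets the passages side by side.

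**Route A, the lead-in.** Section 7.1.2 bars dose 2 for anyone meeting a Section 5.2.1 criterion. Criterion 1 takes its meaning from Table 19, and Table 19 is the pIMD list. A new Table 19 condition before Visit 2 meets criterion 1, so the participant should not be dosed. Guillain-Barré syndrome and narcolepsy reach the same result through criteria 7 and 8, and both also appear in Table 19. There is no judgement step. Criteria 11 and 13 of the same section do rely on the investigator's judgement, so discretion is written into that list where it was wanted.

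**Route B, the last bullet.** A new pIMD is a bar when the investigator sees unacceptable risk. The next sentence calls for judgement before the next dose is administered, so the dose may still be given.

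| New event between doses | Route A | Route B |
|---|---|---|
| Plainly autoimmune Table 19 entry, risk not judged unacceptable | Should not be dosed | Appears open |
| Guillain-Barré syndrome or narcolepsy, risk not judged unacceptable | Should not be dosed | Appears open |
| Table 19 entry without autoimmune cause, risk not judged unacceptable | Should not be dosed on the literal pointer; arguable | Appears open |
| pIMD outside Table 19, risk not judged unacceptable | Reached less directly | Appears open |
| Any pIMD, risk judged unacceptable | Lead-in bars the dose through the bullet itself | Second sentence still asks for judgement |

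The last row shows that the bullet also sits badly with its own lead-in.

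**Effect on the analysis set.** If dose 2 is withheld, the participant leaves PPS1 under either reading, through the Table 9 row for an incomplete course at Visit 2. Only a participant who was dosed can be classified two ways.

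For size, take 57 evaluable participants per cell and the planning rates from Protocol Table 14. Let x be the responder count closest to the planning rate. Excluding one responder changes the rate by (x-1)/56 - x/57. Excluding one non-responder changes it by x/56 - x/57.

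- SPR, 18-64 years (91%), x = 52: 52/57 = 91.23%. Responder out: 51/56 = 91.07%, change -0.16 points. Non-responder out: 52/56 = 92.86%, change +1.63 points.
- SCR, 18-64 years (80%), x = 46: 46/57 = 80.70%. Responder out: 45/56 = 80.36%, change -0.34 points. Non-responder out: 46/56 = 82.14%, change +1.44 points.
- SPR, 65 years and over (86%), x = 49: 49/57 = 85.96%. Responder out: 48/56 = 85.71%, change -0.25 points. Non-responder out: 49/56 = 87.50%, change +1.54 points.
- SCR, 65 years and over (75%), x = 43: 43/57 = 75.44%. Responder out: 42/56 = 75.00%, change -0.44 points. Non-responder out: 43/56 = 76.79%, change +1.35 points.

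At these rates the excluded person is more likely to be a responder, and the change is then under half a point.

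**The case against.** The best defence is that the Section 7.1.2 list is joined by *or*. Each item is sufficient on its own, so the pIMD bullet adds a bar and takes none away. A site that dosed a participant who meets a Section 5.2.1 criterion would be ignoring the lead-in. On this view the bullet still has work to do, because Section 10.3.5.1 allows pIMDs outside Table 19. And since criterion 1 speaks of autoimmune disorders, entries such as gout or Bell's palsy may not fall under it at all.

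Part of this stands. A reader might infer that a new pIMD stops dosing *only* if the investigator sees unacceptable risk; the bullet does not contain that word. The conflict is arguable for entries without an autoimmune cause. The lead-in also says *should not*, not *must not*.

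The defence does not remove the conflict. Under it the bullet has no effect for Table 19 conditions, yet its second sentence still tells sites that the next dose is open. Criterion 1 points to Table 19 without limiting it to autoimmune entries. Plainly autoimmune entries, and the two conditions named in criteria 7 and 8, remain caught by both routes.

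A reader might also infer that site interpretation decides who stays in PPS1. For a dose already given, the documents do not support that. SAP Section 5.2 has deviations identified and classified before the analysis, and SAP Section 4.6.5 has the exclusion rules finalised before the Day 43 interim analysis, partly in the Study Deviation Rules document, which is not available here. That document may define the term for classification, but it cannot cure conflicting dosing instructions to sites.

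**Conclusion.** The inconsistency is in the current text. For a Table 19 condition with onset between the doses, Section 7.1.2 points one way through its lead-in and another through its last bullet. It is clearest for plainly autoimmune entries and for Guillain-Barré syndrome and narcolepsy, and weaker elsewhere.

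The documents give no rate of pIMDs between doses, so the number of participants affected cannot be derived; it is probably small. The case for acting rests on consistent handling of re-exposure, not on power.

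Three larger readings are tempting and should not be drawn:

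- One participant might be thought to move SPR or SCR by 1/57, about 1.75 points. That is the effect of changing one person's response. Exclusion, the mechanism at issue, gives the smaller changes worked out above.
- Amendment 2 might be thought to have created the problem by widening Table 19. Bell's palsy, gout and psoriasis were already in the list that Appendix 8 shows as deleted.
- The conflict might be thought to change PPS1 membership when dose 2 is withheld. It does not.

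The sizes assume 57 evaluable participants, the planning rates, and one exclusion in a cell. No view is taken on which dosing rule is right.

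**What to change.** Reconcile the pIMD bullet in Protocol Section 7.1.2 with the cross-reference to Section 5.2.1, covering criteria 1, 7 and 8, so that one stated rule governs a Table 19 condition with onset after dose 1. An edit that touches criterion 1 alone would leave Guillain-Barré syndrome and narcolepsy in conflict. The bullet's second sentence should also agree with the lead-in.

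Keep the edit narrow. It should not change how a pre-enrolment history discovered later, or a pIMD outside Table 19, is handled unless the sponsor intends that. The clinical choice is the sponsor's.

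Use the same definition of contraindication in SAP Table 9 and in the Study Deviation Rules document, and settle it before the Day 43 analysis. If dosing is already complete, this part is still needed to classify participants who received dose 2.

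The cost is a clarifying sentence in Section 7.1.2 and a matching line in each of the other two documents. No new data are needed, and sample size and analysis method do not change.

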7.2. Participant discontinuation/withdrawal from the study

A participant is considered a ‘withdrawal’ from the study when no study procedure has occurred, no follow-up has been performed and no further information has been collected for this participant from the date of withdrawal/last contact.

From an analysis perspective, a ‘withdrawal’ from the study refers to any participant who was not available for the concluding contact foreseen in the protocol.

Investigators will attempt to contact those participants who do not return for scheduled visits or follow-up.

All data and samples collected until the date of withdrawal/last contact of the participant will be used for the analysis.

The primary reason for study withdrawal will be documented in the eCRF based on the list below:

- Adverse events requiring expedited reporting to GSK
- Unsolicited non-SAE
- Solicited AE
- Protocol deviation
- Withdrawal by participant, not due to an AE*
- Migrated/Moved from the study area
- Lost to follow-up
- Sponsor study termination
- Other (specify)

*If a participant is withdrawn from the study because he/she has withdrawn consent and provided the reason for its withdrawal, the investigator must document this reason in the eCRF.

Participants who are withdrawn from the study because of SAEs/AEs must be clearly distinguished from participants who are withdrawn for other reasons. Investigators will follow participants who are withdrawn from the study as result of an SAE/AE until the event is resolved. (see Section [10.3.8.2](#)).

7.3. Lost to follow-up

A participant will be considered 'lost to follow-up' if he or she fails to return for scheduled visits and is unable to be contacted by the study site.

Please refer to the SPM for a description of the actions to be taken before considering the participant as lost to follow-up.

8. STUDY ASSESSMENTS AND PROCEDURES

Study procedures and their timing are summarized in the SoA (Section [1.3](#)).

Adherence to the protocol is required for study conduct.

Protocol waivers or exemptions are not allowed unless necessary for the management of an immediate safety concerns.

The investigator is not allowed to do testing on samples outside of what has been agreed upon by the Independent Ethics Committee (IEC)/Institutional Review Board (IRB).

Immediate safety concerns should be discussed with the sponsor as soon as they occur or when the study team is aware of them. The purpose of this communication is to determine if the participant(s) should discontinue the study intervention.

All screening evaluations must be completed and the results reviewed before confirming that potential participants meet all eligibility criteria.

The investigator will maintain a screening log of all participants screened. All relevant information, such as confirmation of eligibility and reasons for screening failure will be mentioned in this screening log.

Procedures conducted as part of routine clinical management (e.g. hematologic profiles) and obtained before the participant signed the Informed Consent Form (ICF) may be used for screening and/or for establishing a clinical baseline, provided the procedure met protocol-specified criteria and was performed within the time frame defined in the SoA (Section [1.3](#)).

The SPM provides the investigator and site personnel with administrative and detailed technical information that does not impact participant safety.

8.1. Efficacy and/or immunogenicity assessments

Collected biological samples will be used for protocol mandated research and purposes related to the improvement, development and quality assurance of the laboratory tests described in this protocol.

Future findings may make it desirable to use the samples acquired in this study for future research not described in this protocol. All participants will be asked to give a specific consent to allow GSK or a contracted partner to use the samples for future research. Future research will be subject to prior IEC/IRB approval if required per local legislation.

Information on further investigations and their rationale can be obtained from GSK.

Sample testing will be done in accordance with the recorded consent of the individual participant.

If additional testing is performed, the marker priority ranking given in Section [8.1.3](#) may be changed.

Collected samples will be stored for a maximum of 20 years. This storage period begins when the last participant performed the last study visit, unless local rules, regulations or guidelines require different timeframes or procedures, which would then be in line with participant consent. These extra requirements need to be communicated formally to, and discussed and agreed with, GSK.

